## **Abstract**

### **Background**

Apathy, defined as the absence or lack of motivation and emotional detachment, is a clinical feature of depression. Depressive symptoms and insulin resistance are conditions that are interdependent. We hypothesize that increasing insulin sensitivity in apathetic insulin resistant individuals will reduce apathy. Our preliminary studies show that a low glycemic index (GI) diet and exercise (D+E) intervention for seven days and 12 weeks increases insulin sensitivity in older adults with obesity. The key feature of a low GI diet is its high dietary fiber (DF) content. In preparation for an efficacy trial, we will conduct a dose escalation trial in the elderly with obesity and determine the maximum tolerated dose of a novel DF from whole young soy pods (soy) delivered in soft foods.

### **Design and Method**

#### **Aim**

Determine the maximum tolerated dose of dietary fiber from soy in elderly subjects with obesity and measure fecal short chain fatty acids (SCFA) as a biomarker of compliance.

#### **Hypothesis**

Since this is a dose finding study there is no hypothesis for the maximum tolerated dose; however, fecal SCFA will increase with the dose.

#### **Study Design**

We propose to conduct a dose escalation trial. We will test the tolerability to 10 g, 20 g, and 30 g of soy containing 4 g, 8 g, and 12 g of DF respectively. At each dose, eight subjects will incorporate the foods into their usual diet for one week. We will evaluate tolerability to each dose and measure fecal SCFA as a biomarker of compliance. Subjects who satisfy the eligibility criteria and express willingness to consume the study foods will be enrolled.

At baseline, weight and vital signs will be measured. Subjects will provide a stool sample collected within the last 48 hours and frozen in containers provided for the purpose. Part of the fecal samples will be archived for future analysis. The study dietitian will interview each subject in order to assess the subject's current intake. Based on this information, subjects will be counseled on incorporating the study foods in their diet with the appropriate fluid intake. Subjects will receive the study foods containing 4g DF/10g soy/day for one week and complete a tolerability questionnaire.

Subjects will consume the soft foods containing soy along with their regular diet for one week, and will be advised to return all used and unused containers at the end of the week. Compliance will be assessed from an interview with the subject and an evaluation of used and unused containers returned by subjects. Pre-intervention tests and measures will be repeated, and adverse events will be recorded. If a dose is tolerated, subjects will receive the next escalated dose for one week (8 g DF/20 g soy/day or 12 g DF/30 g soy/day). At the end of each subject's participation in the study, a fasting blood sample will be drawn for evaluation of CBC, and blood chemistry panel as safety markers.

The results of the present study will guide the design and implementation of a clinical trial to determine the effect of a low GI D+E program on insulin sensitivity and apathy in elderly subjects with obesity and insulin resistance. These results will be significant, in that they will potentially provide a cost-effective intervention that will substantially improve the health and quality of life for the growing number of elderly individuals with obesity who have developed insulin resistance and apathy.

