## **STUDY PROCEDURES**

**Whole soy pods (soy).** The plants will be grown under carefully monitored conditions at the LSU Agricultural Center and harvested at reproductive stage six or when the green pods contain soybeans that fill the pods. The whole pods will be processed at the United States Department of Agriculture (USDA, New Orleans, LA), Food Processing and Sensory Quality Research Unit, where scientists work with foods for research purposes. Slicing the pods into thin cross-sections injures plant cells and activates the synthesis of an anti-microbial compound (glyceollin) synthesized by the plant *de novo* in response to stress. Glyceollins have been shown to improve insulin sensitivity and cognition. The sliced pods will be lyophilized and milled. Nutrient analysis, will be performed at Eurofins Food Chemistry Testing (Madison, WI) using methods of analysis of the Association of Official Analytical Chemists.

**Food Development.** The soy will be incorporated in foods and prepared by the PBRC metabolic kitchen. The PBRC metabolic kitchen is staffed with research dietitians who have a primary responsibility to develop foods for research purposes, plan diets, and execute their delivery. In addition, the applicant is a registered dietitian with experience in food development across cuisines and cultures.

**Nutrition Counseling.** Subjects will be counseled by the study dietitian who will interview the subject in order to assess the subject's current intake. Based on this information, subjects will be counseled on incorporating the test foods in their diet. We expect that subjects will experience GI symptoms from increased DF intake, but from the applicant's practice as a

registered dietitian and evidence in the literature we know that these symptoms resolve. To enhance compliance with the protocol, subjects will receive counseling on managing GI symptoms.

**Food Tolerability.** Subjects will complete a version of the GI symptoms questionnaire designed as a validated assessment for dyspepsia, and modified to make it specific by only including the symptoms that may be experienced with high DF intake. The scale is ranked as none, mild, moderate, and severe for each of four GI symptoms (bloating, abdominal rumbling, flatulence, and abdominal pain). Additionally, subjects will report their stool frequency ranging from 0 to 9+, and stool consistency based on the Bristol Stool scale.

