## **SAMPLE SIZE AND ANALYSIS**

The primary objective of the study is to determine the maximum tolerated dose of DF. Six subjects at each dose are sufficient to detect tolerability. However, we will enroll 10 subjects to test each dose of DF from soy. Dose safety will be investigated by compiling by treatment (e.g. 4 g dose, 8 g dose, 12 g dose) a list of adverse events such as frequency of headaches, nausea, vomiting. For GI symptoms the scale is ranked as none (no symptoms), mild, moderate, and severe for each of four GI symptoms and the assessment of intensity is provided in the data safety monitoring plan. Moderate and severe ratings will be considered intolerance to the dose. Stool frequency of one to three/day, or three times/ per week is considered regular. Therefore, stool frequency of less than one and more than nine over a 72 hour period will be a consideration for determining intolerance. Stool consistency of Type three to five on the Bristol Stool Scale is considered normal. Any other rating will be considered in the determination of intolerance. To be considered intolerance, subjects must rate stool frequency and consistency as being of moderate to severe intensity.

According to the NCI convention for dose limiting toxicity to a drug, 1) if two out of three (66%) subjects are intolerant to the dose, the next lower dose is the maximum dose tested; and 2) if one out of three (33%) are intolerant to a dose, then that dose is considered the maximum tolerated dose. Therefore for a food, 1) if five out of eight (63%) are intolerant, we will adopt the next lower dose; and 2) if three out of eight (37%) are intolerant to a dose, then that dose will be taken as the maximum tolerated dose.

A mixed effect linear model will be used to estimate changes in the fecal SCFA while accounting for subject correlation across time using all available data. The outcome will be within subject changes over time.

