### **WITHDRAWAL OF SUBJECTS**

We will attempt to retain program participants once randomized for study completion through the end of study visit. It is our desire to analyze results on all participants who were enrolled in the study. In accordance with the declaration of Helsinki/Tokyo/Venice/Hong Kong, participants have the right to withdraw from the program at any time for any reason. The investigator also has the right to withdraw participants from the program treatments in the event of inter-current illness, adverse experience, treatment failure, protocol violation, or other reasons. Should a participant decide to withdraw from treatment, all efforts will be made to complete and report follow-up observations as thoroughly as possible.

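### Intake data do not enter the intolerance count, so a subject who ate too little to have symptoms counts as tolerating the dose; this can push the MTD upward

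*Combined protocol and SAP*

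**What the plan says.** **Definition of intolerance.** Under Food Tolerability in Study Procedures, "The scale is ranked as none, mild, moderate, and severe for each of four GI symptoms": abdominal pain, flatulence, rumbling and bloating. Sample Size and Analysis then says "Moderate and severe ratings will be considered intolerance to the dose". Stool measures carry their own condition: "To be considered intolerance, subjects must rate stool frequency and consistency as being of moderate to severe intensity". Section 2.0 (Interim Analysis) of the data safety monitoring plan repeats these definitions.

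**Dose rule.** In Sample Size and Analysis, "if five out of eight (63%) are intolerant, we will adopt the next lower dose", and "if three out of eight (37%) are intolerant to a dose, then that dose will be taken as the maximum tolerated dose". The same section says "However, we will enroll 10 subjects to test each dose of DF from soy".

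**Intake.** Study Design says "Compliance will be assessed from an interview with the subject and an evaluation of used and unused containers". Fecal SCFA is the compliance biomarker, and its only planned analysis is a mixed model of change. No minimum intake is given, and neither the intolerance definition nor the dose rule refers to intake.

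**Order of assessments.** In the Visit 1 and Visit 2 sections and Table 1, the tolerability questionnaire is done by phone the day before the visit. The Visit 1 section explains that this saves preparing food for someone who does not tolerate the dose. Kitchen staff assess compliance at the visit itself.

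**Withdrawal.** Withdrawal of Subjects says "Should a participant decide to withdraw from treatment, all efforts will be made to complete and report follow-up observations as thoroughly as possible", and expresses a wish to analyze everyone enrolled. It does not say how a withdrawn subject enters the MTD count.

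**The concern.** For a food, failing to eat it can itself be a sign of intolerance. It also removes the exposure that would produce the rated symptoms. A subject who ate little and rates symptoms as none or mild meets the written definition of tolerating 8 g or 12 g without having taken that amount. For this subject the stated rule gives a wrong classification; the trouble is more than a missing detail. The call that informs preparation of the next dose is made before anyone has looked at the containers, so the schedule does not correct it.

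The MTD is the primary aim, and the results are meant to guide the later efficacy trial. The plan itself expects gastrointestinal symptoms from the added fiber, so eating less in response is plausible. An MTD set too high would be carried into that trial.

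**Working it through.** **1. The plan's own figures.** 5/8 = 62.5% (printed as 63%) and 3/8 = 37.5% (printed as 37%). Both agree within rounding or truncation. The plan gives no assumed intolerance rate, error rate or power, so the statement that six subjects per dose suffice cannot be recomputed.

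**2. Effect on the count.** Suppose five of eight are truly intolerant and k of them show it only by uneaten food or withdrawal.

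| k missed | Counted, kept in denominator | Removed from denominator |
|---|---|---|
| 0 | 5/8 = 62.5% | 5/8 = 62.5% |
| 1 | 4/8 = 50% | 4/7 = 57.1% |
| 2 | 3/8 = 37.5% | 3/6 = 50% |

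With one missed, the count for the next lower dose is not met, and the plan states no outcome for 4/8. With two missed and all eight kept, the count equals the one that names the dose the MTD. Removing missed subjects from the denominator gives a smaller shift, still downward.

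**3. Chance of reaching five of eight.** Let p be the true intolerance rate and m the share of intolerant subjects missed. Both are assumptions, as the documents give neither. The counted rate is q = p(1 − m). Reading the rule as five or more, P = Σ (x = 5 to 8) C(8,x) qˣ(1 − q)⁸⁻ˣ. For example, p = 0.625 and m = 0.20 give q = 0.50 and P = (56 + 28 + 8 + 1)/256 = 0.363.

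| True p | m = 0 | 10% | 20% | 30% | 50% |
|---|---|---|---|---|---|
| 0.50 | 0.363 | 0.260 | 0.174 | 0.106 | 0.027 |
| 0.625 | 0.651 | 0.506 | 0.363 | 0.237 | 0.068 |
| 0.70 | 0.806 | 0.663 | 0.500 | 0.342 | 0.106 |

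**4. With the ten subjects enrolled.** At p = 0.625 and m = 20%, a fixed count of five of ten is reached with probability 0.872 if none are missed and 0.623 otherwise. If the cut-off is read as a proportion, 0.625 × 10 = 6.25, so seven are needed; the probabilities are 0.447 and 0.172. The direction is the same, but the level depends on a denominator that the plan leaves unsettled.

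**5. Error the other way.** Counting all non-intake as intolerance would overcount. If p = 0.30 and 10% of tolerant subjects leave food or withdraw for unrelated reasons, the counted rate is 0.30 + 0.70 × 0.10 = 0.37. P(five or more of eight) then rises from 0.058 to 0.131. A repair has to separate the reasons for low intake.

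**The case against.** A reader might infer that anyone who stops eating or withdraws is scored as tolerating the dose. The documents do not support that.

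- A subject who stops because of symptoms and rates them moderate or severe is already counted. Section 1.2 of the monitoring plan describes mild as easily borne with minimal discomfort, which hardly fits a gut upset that makes someone abandon the food. The recall period of the questionnaire is not given, so it cannot be assumed to miss symptoms from early in the week.
- A withdrawn subject is unclassified. The text would allow intolerant, missing or replaced. Against a fixed count of five, leaving the subject out has the same effect as scoring tolerant, but that is an inference.
- Adverse events, including nausea and vomiting, are listed by dose. The PI discusses tolerability with the Safety Officer during titration (section 3.2), and the Safety Officer may review protocol adherence (section 3.7).

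The first two points stand and narrow the gap to subjects who ate less and so had few symptoms, those who refused for taste, volume or a symptom off the four-item scale, and those who withdrew. The third is a real safeguard against such a subject going unnoticed, but none of these steps contains a criterion on intake or withdrawal, and none alters the count.

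It is also fair to object that the size of the effect rests on a share that nobody knows. That is why a range is shown.

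**Conclusion.** The concern holds in limited form. Following the rule as written, a subject who ate too little to have symptoms counts as tolerating the dose, and a subject who withdraws has no stated classification. The MTD can be biased upward when the dose causes the low intake or withdrawal.

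A firmer claim, that the MTD will be inflated, goes beyond the documents: the missed share is unknown, and low intake for unrelated reasons is not missed intolerance. What needs no assumption about that share is the fragility of the count, since one or two missed cases among eight change the outcome. The probabilities further assume independent subjects with a common intolerance rate and a rule read as five or more of eight. The point merits a change before enrolment.

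**What to change.** In Sample Size and Analysis and in section 2.0 of the monitoring plan, for the MTD analysis only:

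1. Fix before enrolment the minimum share of dispensed food that a subject must have eaten to be evaluable as tolerant at a dose.
2. Count as intolerant any subject who stopped the food, withdrew or fell below that share with symptoms given as the reason.
3. Treat low intake for other reasons as not evaluable at that dose.
4. State the cut-offs as proportions of evaluable subjects, with the rounding, and reconcile the rule written for eight with the enrolment of ten. Without this, step 3 leaves the 5/8 and 3/8 counts undefined when fewer than eight are evaluable.
5. Report the MTD count with and without this rule.

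The cost is a few sentences. The container check and interview are already planned; the interview must record the reason for low intake. The intake cut-off is a convention, and the paired display shows how much depends on it.

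Tolerance also governs each subject's move to the next dose. How intake bears on that is for the sponsor to reconcile across Study Design, Clinic Visits, the Visit 1 section, and sections 2.0 and 3.2 of the monitoring plan. No dosing rule is proposed here.

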## DESCRIPTION AND RATIONALE

[figure not shown]
The US population is expected to be comprised of approximately 24% older adults (> 65 years) by 2050. More than 35% of US adults over 60 years of age are obese and nearly half of older adults are insulin resistant. Depressive symptoms, which have an incidence of 6.8 per 100 person-years in the elderly (> 70 years), and insulin resistance are conditions that are interdependent; yet, the effect of improving insulin sensitivity on depressive symptoms such as apathy has not been investigated.

### Apathy.

Apathy is a motivation disorder that results in diminished goal directed behavior, lack of concern about one's health, and emotional indifference. Apathy occurs in more than 30% of individuals with major depression and is most prevalent in depressed older adults. The prevalence of apathy in the absence of clinical depression in cognitively-intact older adults (Geriatric Depression Scale [GDS] endorsed apathy items  $\geq 2$ ) ranges from 14% to 26%. Impaired glucose metabolism is associated with depressive symptoms, particularly in the elderly (Figure 1). The biological link between depression and insulin resistance appears to be an overactive dysregulated hypothalamic-pituitary-adrenal (HPA) axis. The resulting hypercortisolemia promotes obesity and insulin resistance. Since insulin resistance and depressive symptoms are interdependent, improving insulin sensitivity has therapeutic potential in the treatment of apathy. The presence of apathy predicts chronicity of depression, poor response of depressive symptoms to treatment, and it is associated with disability that transcends the rest of the depressive syndrome. Apathy is a source of significant burden on the caregiver and current interventions lack the precision needed to address apathy and its underlying mechanisms. Identifying distinct pathways for intervention will guide the course of treatment and facilitate customized interventions for a pressing, unmet, aging need.

**Exercise and Insulin Resistance.** The literature supports the benefits of exercise on insulin sensitivity in the overweight and obese elderly. Different doses of aerobic exercise ranging from 90 minutes/week to 300 minutes/week have been shown to improve insulin sensitivity. Adherence to the exercise prescription varies across the studies and the dose that would most likely foster compliance with a regimen, and yet be effective, remains unclear. The appropriate exercise regimen for older insulin resistant individuals that will be of relevance in real-world clinical practice settings constitutes a significant gap in the literature. Further, the effects of exercise on apathy are unexplored; but, evidence lends support to the usefulness of exercise in treating depression and preventing its onset.

**Diet and Insulin Resistance.** Some food sources of carbohydrates have a lower potential to raise blood glucose concentrations than other carbohydrate-rich food sources. This potential of individual foods, is measured by the glycemic index (GI), which provides a numerical value to represent the effect of the food on blood glucose concentrations. In a tightly controlled study, a low GI diet and exercise (D+E) based lifestyle intervention for 12 weeks improved insulin sensitivity in obese insulin resistant older adults. Supplementing the high GI diet with dietary fiber (DF) produced similar results. The key feature of the low GI diet is its high DF content. Another randomized controlled trial (RCT) showed that a low GI diet that included legumes high in soluble DF reduced glycosylated hemoglobin ( $\text{Hb}_{\text{A1C}}$ ) in subjects with type 2 diabetes, but the improvements in glycemia did not differ from a regular diet high in insoluble wheat DF. Thus, the DF content of a low GI diet appears to be an important mediator of its effects on glucose metabolism.

**Figure 1. Relationship between insulin resistance and apathy**

**Dietary Fiber in Soybean.** The whole pods of young soybean (edamame) provide approximately four times the DF in an equivalent amount of the green soybean. A high-DF diet prevents the stress related rise in cortisol. The majority of the clinical and epidemiologic evidence supports the anti-depressive effects of diets high in soybeans. Observational studies in Asian populations showed an association between soybean consumption and reduced incidence of type 2 diabetes and cardiovascular disease. A meta-analysis of nine RCTs determined that consumption of whole soy products, reduced hyperglycemia. Including soybean in a Western diet in the amounts consumed in Asian cultures poses a challenge. However, milled to a flour the whole pods of young soybean (soy) taste like other legume flours, and contain far more DF. Moreover, soy contains DF, protein, isoflavones, and phytochemicals in their original proportions. In rodents, soy increases fecal fat and glucose excretion, and the synthesis of short chain fatty acids (SCFA). Therefore, we hypothesize that soy will potentiate the effects of a low GI diet on insulin sensitivity.

**Summary.** Depressive symptoms, which are common in the elderly (> 70 years), and insulin resistance are conditions that predispose to each other. Therefore, improving insulin sensitivity may be beneficial in reducing depressive symptoms in the obese elderly. Apathy, being a common depressive symptom in the elderly and among individuals with diabetes, represents a particularly attractive therapeutic target for interventions designed to improve glucose metabolism. A low glycemic index (GI) diet and exercise (D+E) intervention increases insulin sensitivity in obese older adults. To maintain the benefits of a low GI diet in the elderly, foods must be DF-dense, yet soft and tasty. The effect of whole pods of young soybean (soy) on insulin sensitivity has never been explored in humans. In preparation for conducting an efficacy trial of the effect of soy on insulin sensitivity, we will first conduct a dose escalation study in an elderly population to determine the maximum dose of fiber from soy that will be tolerated.

## HYPOTHESIS AND SPECIFIC AIMS

Edamame or green soybean in the pod has approximately four times more dietary fiber than soybean without the pod. The whole soy pod (soy), rich in phytonutrients, increases fecal fat and glucose excretion and the synthesis of short chain fatty acids in mice. The majority of the clinical and epidemiologic evidence supports the anti-depressive effects of diets high in soybeans. In previous controlled feeding and exercise studies, we found that a low GI D+E for one week (n = 32) or 12 weeks (n = 22) increases insulin sensitivity in older adults with obesity. These data form the basis of a proposal to test the hypothesis that insulin sensitivity mediates apathy in depression. No study to date has empirically tested this hypothesis. The success of the efficacy trial depends on a determination of the optimal dose of dietary fiber from soy that will be tolerated by the elderly. Therefore, the present study will determine the maximum tolerated dose of dietary fiber from soy. The results will inform the development of a randomized controlled trial (RCT) to test the efficacy of a low GI D+E program (with and without soy) to increase insulin sensitivity and reduce apathy in the elderly.

**Aim.** Determine the maximum tolerated dose of dietary fiber from soy in elderly subjects with obesity. This aim requires a dose escalation trial in the elderly with obesity. We will test the tolerability to soft foods including 10 g, 20 g, and 30 g of soy containing 4 g, 8 g, and 12 g of dietary fiber, respectively. At each dose, eight subjects will consume the foods for one week. We will evaluate tolerability to each dose and measure fecal short chain fatty acids as a biomarker of compliance with the intervention.

**Hypothesis:** Since this is a dose finding study there is no hypothesis for the maximum tolerated dose; however, fecal short chain fatty acids will increase with the dose.

